2.4. Pre- and post-intervention assessments

Once an informed consent is obtained prior to randomisation; participants will be referred to study examiners - a Physical Medicine and Rehabilitation physician, a neurologist, a physical therapist, an occupational therapist and a psychologist, who will not know the treatment group of the patient. They will administer baseline testing during the 2nd and 3rd day after admission to the department (Pre-assessment). The Post-assessment 1 will be done at the end of the three-week inpatient intensive comprehensive rehabilitation (during the last two days of hospitalization). Follow-up assessments will take place 3 and 12 months after the admission, respectively, by a telephone interview and hospital visit for blood draw. The aim is to be assessed only by one examiner, in case of more examiners, inter-rater reliability will be assessed (Table 2).

test	abbreviation	Inclusion and exclusion criteria	Examination No			
			1	2	3	4
			baseli	+3	+3	+ 1
			ne	weeks	month s	year
Neurologist						
Demographic and anamnestic data (age, after first ischemic stroke, days after the stroke) Demographic and anamnestic data (weight and height, cardiovascular risk factors, Bamford classification, medication)			x			
Modified Rankin Scale	mRS	Х		х		
Pre-Stroke Modified Rankin Score	pre-stroke mRS	Х				
Historic Stroke Motor Severity Score	HSSS	Х				
National Institute of Health Stroke Scale	NIHSS	Х				
Psychologist*						
Montreal Cognitive Assessment	MoCA		Х			
Amnesia Light and Brief Assessment	ALBA		х	х		
NEO-Five Factor Inventory	NEO - FFI		х			
Patient-reported Outcomes Measurement Information System Global Health	PROMIS		х	х	х	х
the World Health Organization Disability Assessment Schedule	WHODAS		Х	Х	Х	Х

Table 2: Timing and distribution of examination in the team

the Goal Attainment scale	GAS				
Picture naming and immediate recall	PICNIR	х	х		
Neuro - QOL depression		х	х		
physical therapist					
Hand Dynamometer		Х	Х		
postural tremor		х	х		
Action Research Arm Test*	ARAT	х	х		
Motor Activity Log*	MAL	х	x		
Timed Up and Go*	TUG	х	x		
Berg Balance Scale*	BBS	х	x		
The 10 Metre Walk Test*		x	х		
The 6 Minute Walk Test*		x	х		
Functional Independence Measure*	FIM	х	х		
Laterality index	LI	х			
Nine Hole Peg Test		х	х		
speech therapist*					
The Gugging Swallowing Screen	GSS	Х	х		
The 3F Test – Dysarthric Profile	3F test	х	х	-	
Dysan		х	х		
The Mississippi Aphasia Screening	MAST	х	х		
Test					
Image Naming Test	INT	Х	X		

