2.6. Estimated size

It is estimated that approximately 110 people will be recruited to the clinical trial each year. This number is based on the fulfilment of performance and quality indicators report of cerebrovascular care at the Centre for Highly Specialized Patient Care for Stroke Patients at Thomayer Hospital 2019. A total of 210 people is expected to be enrolled in the clinical trial over a period of two years (Figure 2), corresponding to a required sample number of 70 patients per group. This value is necessary in order to detect a significant difference in improvement

between two groups when achieving a mean difference effect (Cohen's d = 0.5), a significance level of $\alpha = .05$ and a strength of $1-\beta = .80$. The sample size was determined based on the minimal clinically significant change on a Berg balance scale (96).

Figure 2: Planned recruitment and randomisation process

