2.9. Measuring the effectiveness of rehabilitation

To test hypothesis I., i.e., a positive influence on all outcomes, the effect of therapy for each therapeutic group will be assessed separately by paired t-tests performed on pre-test and post-test scores. The Wilcoxon rank test will be used on data where normal distribution cannot be expected.

To test hypotheses II. and III, a comparison between therapeutic groups will be performed using two sample Student t-tests on differences between measurement time points (or Wilcoxon tests respectively for data, where normal distribution of the differences cannot be expected). For hypothesis II, the COMIRESTROKE - ICF group will be compared against the rest of the participants. For hypothesis III, the COMIRESTROKE - NEFI group will be compared against the rest of the participants. A one-sided alternative will be tested according to our hypotheses. We will also implement the one-way ANOVA test to jointly compare all three groups for prepost differences. In addition, a Tukey post-hoc comparison will be made to detect any further group differences beyond our hypotheses.

To assess the overall impact of rehabilitation and to compare effectiveness of different therapeutic approaches for Hypotheses I – III in more complex way, and to test for effect of other covariates in Hypothesis IV, a linear mixed effect model will be used with random patient effect fitted to longitudinal patient data. Measurement effect, group effect and their interaction, as well as effects of other covariates such as the level of disability in admission time will be tested by F test.

To address Goal I, correlations between changes in different examination scores will be evaluated using Pearson correlation coefficient and its nonparametric analogies. A cluster analysis will be performed to identify different phenotypes. This will allow the identification of different groups of patients in relation to the efficacy of the neuro-rehabilitation programs.

To address Goal II, for selected multi-item instruments, item-response theory (IRT) and generalized linear regression models will be used to study differential item functioning with respect to rehabilitation groups. Account will be taken for other respondent characteristics. Use will be made of differential item functioning in change (DIF-C) analysis (7) in order to detect between-group differences.

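### Section 2.9 tests Hypotheses I–III on complete pairs and leaves the mixed model for the same hypotheses unranked; the avoidable bias lies mainly in the follow-up part of Hypothesis II

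*Combined protocol and SAP*

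**What the plan says.** Section 2.9 sets out two layers of analysis for the same hypotheses.

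- **Hypothesis I:** each therapeutic group is assessed separately "by paired t-tests performed on pre-test and post-test scores".
- **Hypotheses II and III:** "two sample Student t-tests on differences between measurement time points", setting one arm against everyone else. "A one-sided alternative will be tested according to our hypotheses".
- **In addition:** a "one-way ANOVA test to jointly compare all three groups for prepost differences".
- **Then, for Hypotheses I–III again and for Hypothesis IV:** "a linear mixed effect model will be used with random patient effect fitted to longitudinal patient data", with F tests of measurement, group and their interaction. Its stated purpose includes "to compare effectiveness of different therapeutic approaches for Hypotheses I – III in more complex way".

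Rank-based tests replace the t-tests where normality is doubtful. Section 2.7 also sends any observed baseline differences to the longitudinal models.

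On timing, section 2.4 says: "The Post-assessment 1 will be done at the end of the three-week inpatient intensive comprehensive rehabilitation". Section 2.1 limits the 3- and 12-month examinations to the primary outcomes. Table 2 marks PROMIS and WHODAS at all four visits, and the repeated secondary tests and the blood sample at baseline and 3 weeks only (the text of section 2.4 also mentions a blood draw at follow-up).

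The plan does not say which analysis decides a hypothesis. It also has no analysis population, no missing-data rule, no expected dropout and no rule for assessing a patient who leaves the programme early.

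**The concern.** A change score needs both values. A patient without the later measurement contributes nothing to the paired tests, the two-sample tests or the ANOVA for that interval. The mixed model can use whatever visits the patient has. Once data are missing, the two layers describe different patients and can give different answers. They differ even with complete data, because the t-tests are one-sided contrasts of one arm against the others, whereas the model is read through F tests. With no ranking, the choice can be made after the results are seen.

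Unequal loss is plausible here. Three arms have four hours of therapy a day and the fourth has standard care. Section 2.3 describes a referral to an outpatient programme after the ICF arm and undirected care after the NEFI programme. If patients who respond poorly early on are lost more often from one arm, the completer comparison flatters that arm. Hypothesis II reaches out to 3 and 12 months, where losses have had most time to build up.

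**Working it through.** **1. The plan's own figure.** Section 2.6 gives 70 per group for d = 0.5, alpha 0.05 and power 0.80. The usual formula gives n = 2(1.960 + 0.842)²/0.5² = 62.8, so 63 (64 with the t distribution). A 10% loss allowance would give 63/0.90 = 70, but section 2.6 states no allowance. The 70 therefore cannot be read as the plan's expected dropout, and loss rates below are assumptions.

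**2. Which comparisons are exposed.**

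- Hypothesis I, paired pre-post tests: only a missing baseline or 3-week value matters.
- Hypothesis III, secondary outcomes and lncRNA: essentially baseline and 3 weeks, so again only those values matter.
- Hypothesis II: the 3-week comparison as above, plus the 3- and 12-month comparisons. Only here can a patient have a useful intermediate value (3 weeks) and still drop out of the named test.

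**3. Size of the completer bias at 12 months.** Assume no true effect and loss after week 3. The log-odds of loss fall by b per SD of 3-week change Z. For normal scores, the mean of Z among those who stay is b·E[p(1−p)]/(1−d), roughly b·d, where p is the individual probability of loss and d the arm's loss rate. If r is the correlation of the 3-week change with the 12-month change, then

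bias ≈ r × b × (d_A − d_B), in SD of change.

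Take correlations of 0.6 (baseline with 3 weeks), 0.4 (baseline with 12 months) and 0.6 (3 weeks with 12 months), all assumed. Then r = (1 − 0.6 − 0.4 + 0.6)/√(0.8 × 1.2) = 0.6/0.98 = 0.61.

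| Loss | b | Approximation | Simulated range |
|---|---|---|---|
| 10% vs 30% | 0.5 to 1 | 0.06 to 0.12 | about 0.05–0.10 |
| 15% vs 25% | 0.5 to 1 | 0.03 to 0.06 | about 0.03–0.05 |
| equal | any | 0 | about 0 |

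The simulations used four visits with correlations of 0.4–0.8 and 0.6–0.8. The approximation runs slightly high at b = 1. If loss depends on the 3-week level rather than the change, the bias is 0.03 SD or less.

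**4. What the model removes.** With loss of 10% vs 30%, a model with only a random patient effect, which implies equal correlation between all visits, left 0.016–0.033 SD of a completer bias of 0.05–0.10 SD. Over both loss scenarios it left about 0.01–0.03 SD, or a fifth to a third. A model with the correct visit covariance left about 0.

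**5. Effect on the test.** A separate simulation used 70 vs 140 patients, a steeper dependence (b = 1.5, rescaled to the target loss), and 30% loss in the smaller group against 10%. The t-test had bias 0.098 SD and two-sided error 0.089; the likelihood model with known covariance had bias 0.000 and error 0.049. For the planned one-sided test, 49 and 126 patients remain. With a baseline to 12-month correlation of 0.47, the SD of change is √(2 × 0.53) = 1.03. The standard error is 1.03 × √(1/49 + 1/126) = 0.173, and 0.098/0.173 = 0.57. The one-sided error is then 1 − Φ(1.645 − 0.57), about 0.14 at nominal 0.05. At 20% vs 10% (bias 0.048, 56 and 126 remaining, standard error 0.165) it is about 0.09. This inflation arises when the hypothesised arm is the one with more loss; the reverse makes the test conservative.

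**6. Two-visit outcomes.** A patient without the 3-week value contributes only a baseline. The model then corrects only for loss that the baseline predicts. With 30% vs 10% loss driven by baseline, the t-test bias was −0.075 SD and the model's 0.001. Loss that follows progress during the programme leaves nothing observed for the model to use.

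**The case against.** Several points can fairly be made for the plan, and some stand.

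- **A reader might infer that anyone who stops the programme leaves the analysis.** The documents do not say so. A missing measurement removes a patient; stopping does not. Someone who stops but answers the 12-month call stays in that comparison. Tying Post-assessment 1 to the last days of the stay does not clearly exclude an early discharge either. The text is silent.
- **A reader might infer that a patient lost at 3 or 12 months disappears from all the tests for Hypotheses I–III.** That is not supported. The Hypothesis I test is pre-post, and Hypothesis III rests on outcomes that are essentially not collected at follow-up. Even under Hypothesis II the patient remains in the 3-week comparison.
- **A reader might infer that the mixed model has no role.** It is assigned to Hypotheses I–III and is the method for Hypothesis IV. It is also the only named method that could address superiority over control in Hypothesis I, since the paired tests are within group and the ANOVA is described for three groups. What it lacks is rank.
- **The bias is modest and depends on assumptions.** At 15% vs 25% loss it is 0.03–0.05 SD, against a standard error of √(1/70 + 1/140) = 0.15 SD before losses. This stands, and limits the weight of the point.
- **Promoting the model exactly as planned would not remove all of the bias.** This also stands, and is why the covariance belongs in the fix.

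None of this answers the central gap: complete-pair tests and a mixed model address the same hypotheses, and nothing says which decides.

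**Conclusion.** The point holds in limited form. The named tests for Hypotheses I–III are complete-pair analyses, and the mixed model for the same hypotheses is unranked. The avoidable bias is mainly in the 3- and 12-month primary-outcome comparisons of Hypothesis II: about 0.05–0.10 SD (10–20% of the planned d = 0.5) at 10% vs 30% loss, about 0.03–0.05 SD (6–10%) at 15% vs 25%, and about 0 at equal loss.

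These figures assume the loss rates, the visit correlations, and loss driven by 3-week change; the plan supplies none of them. They describe an outcome scored at all four visits, such as PROMIS or WHODAS. The GAS goal types follow different schedules and are not directly covered. For outcomes measured only at baseline and 3 weeks, the mixed model recovers little when loss follows progress during the programme, so the gain there is chiefly a fixed choice of analysis. This is a change that should be made, not one on which the trial's validity turns.

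**What to change.** Before unblinding, amend section 2.9, with matching wording in section 2.4:

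- Name the mixed model as the deciding analysis for the between-group comparisons in Hypotheses I–III, with pre-specified group-by-visit contrasts that state the arms, visit and sidedness. Make the t-tests supportive.
- Fit it to all randomised patients as assigned, using every available measurement of the outcome analysed.
- Use an unstructured covariance across visits, available in the nlme library named in section 2.10, instead of only a random patient intercept.
- State the missing-at-random assumption and add a sensitivity analysis that departs from it. This matters most for the two-visit outcomes.
- State that patients who stop the programme still receive the planned assessments and calls.
- Report losses, with reasons, by arm and visit.

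The cost is wording plus one sensitivity analysis; the model, library and calls are already planned. The small downside is that the headline result comes from a model rather than a simple t-test.

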2.8. Hypotheses

This clinical trial will test the following scientific hypotheses:

I. COMIRESTROKE under all three settings has a positive influence on all outcomes and higher effect than control group.

II. COMIRESTROKE - ICF will have the highest impact on primary outcomes (GAS, PROMIS, WHODAS 2.0) and on such secondary outcomes that were identified as treatment goals. Furthermore, we expect the highest impact on the primary outcomes in the follow-up (three and twelve months after finishing the rehabilitation).

III. COMIRESTROKE – NEFI will have the highest effect on the secondary outcomes, mainly on motor functions. Moreover, it will most significantly lead to the initiation of plastic and adaptive processes, assessed by the level of lncRNAs in the peripheral blood.

IV. The most important predictor of effective rehabilitation will be the level of disability at admission time; however, the content of the rehabilitation will have an impact on perceived, clinical, and physiological changes of the rehabilitant.

The exploratory goals of this clinical trial are as follows:

Goal I - Improvement patterns: Considering the high number of measured outcomes, for a deeper understanding of therapy efficacy with respect to patient and treatment characteristics, this clinical trial will aim to identify groups of patients with similar improvement patterns post therapy.

Goal II - Item-level analysis: To provide a deeper understanding of the differences in effectiveness between the three therapeutic approaches, this clinical trial will plan to explore item-level between-group differences in improvement.

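### Hypotheses II and III each call one programme the highest, but the planned test against the pooled remaining participants can only show it is above their average

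*Combined protocol and SAP*

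**What the plan says.** Section 2.8 states two superlative hypotheses. Hypothesis II: "COMIRESTROKE - ICF will have the highest impact on primary outcomes (GAS, PROMIS, WHODAS 2.0" and on those secondary outcomes that were set as treatment goals. Hypothesis III: "NEFI will have the highest effect on the secondary outcomes, mainly on motor functions".

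Section 2.9 says how they are tested: "a comparison between therapeutic groups will be performed using two sample Student t-tests on differences between measurement time points", with a Wilcoxon test where normality is doubtful and with a one-sided alternative. The comparator is the same for both: "For hypothesis II, the COMIRESTROKE - ICF group will be compared against the rest of the participants" and "For hypothesis III, the COMIRESTROKE - NEFI group will be compared against the rest of the participants".

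Three further analyses follow in section 2.9:

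- An ANOVA: "We will also implement the one-way ANOVA test to jointly compare all three groups for prepost differences".
- Pairwise comparisons: "a Tukey post-hoc comparison will be made to detect any further group differences beyond our hypotheses".
- A linear mixed model, tied to Hypotheses I to III, in which "Measurement effect, group effect and their interaction, as well as effects of other covariates" are tested by F test.

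Section 2.1 and the Randomisation paragraph describe four arms allocated 1:1:1:1, with Group 4 receiving standard care.

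**The concern.** Being highest means exceeding each other arm. A comparison of one arm with all remaining participants pooled has a different null: that the arm is not above the average of the others. Rejecting it leaves open that another arm is equal or better.

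The comparator is also undefined. Read literally in a four-arm trial, the remaining participants include Group 4. But section 2.9 also speaks of therapeutic groups and of three groups, and section 2.3 refers to two remaining cohorts, so only the other two programmes may be meant. Two analysts could run different tests of the same hypothesis.

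At stake is the headline claim of the trial, because Hypothesis II is the one that names the three primary outcomes. ICF could be reported as best when it only ties with TECH or is worse. If control is pooled, it could be reported as best merely because standard care pulls the comparator down. The same holds for NEFI under Hypothesis III.

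**Working it through.** **The plan's own figure.** Section 2.6 gives 70 per group and 210 in total for d = 0.5, α = .05 and power .80 between two groups. The usual formula is n = 2(z_α + z_β)²/d².

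- Two-sided: 2(1.960 + 0.842)²/0.25 ≈ 62.8, so 63 (64 with the t distribution).
- One-sided: 2(1.645 + 0.842)²/0.25 ≈ 49.5, so 50 (51 with the t distribution).

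The figure of 70 follows from the two-sided 63 only with an unstated allowance of about 10% (63/0.90 = 70). Either way it was set for a pairwise comparison, not for one arm against a pool. Also, 210 = 3 × 70, whereas four equal arms give 210/4 = 52.5 each.

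**What the test estimates.** With equal arms, the t-test contrast is the arm's mean change minus the plain average of the other arms' means. Its standard error in SD units is:

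- control pooled: √(1/52.5 + 1/157.5) = 0.159
- TECH and NEFI only: √(1/52.5 + 1/105) = 0.169

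The chance of a significant one-sided result is about P(Z > 1.645 − contrast/SE). Two examples:

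- Three programmes equal at 0.5 SD, control 0, control pooled: contrast 0.5 − (0.5 + 0.5 + 0)/3 = 0.167; 0.167/0.159 = 1.05; P(Z > 0.60) ≈ 27%.
- ICF and TECH at 0.5, NEFI 0, control left out: contrast 0.5 − (0.5 + 0)/2 = 0.25; 0.25/0.169 = 1.48; P(Z > 0.17) ≈ 43%.

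Simulation gives slightly lower values (26% and 41%), because differences between arms inside the pool widen its spread.

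**Simulation.** 200,000 trials per row; arm sizes 53, 53, 52, 52; change SD 1; one-sided .05; pooled-variance t-tests. The arm means are assumptions. The last column requires ICF to beat each of the three other arms separately at one-sided .05.

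| Means: ICF, TECH, NEFI, control | ICF vs all others | ICF vs TECH + NEFI | ICF beats each arm |
|---|---|---|---|
| 0.1, 0.1, 0.1, 0 | 8% | 5% | 0.8% |
| 0.2, 0.2, 0.2, 0 | 11% | 5% | 1.0% |
| 0.3, 0.3, 0.3, 0 | 15% | 5% | 1.1% |
| 0.5, 0.5, 0.5, 0 | 26% | 5% | 1.2% |
| 0.8, 0.8, 0.8, 0 | 47% | 5% | 1.2% |
| 1.0, 1.0, 1.0, 0 | 62% | 5% | 1.2% |
| 0.5, 0.5, 0, 0 (tie with TECH) | 65% | 41% | 4.9% |
| 0.5, 0.6, 0.3, 0 (worse than TECH) | 33% | 8% | 1.1% |
| 0.5, 0.7, 0, 0 (worse than TECH) | 48% | 20% | 0.4% |

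In none of these rows is ICF uniquely highest, so every significant result would support a false claim.

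**More patients make it worse.** At 70 per arm (280 in total), the equal-programme rows at 0.3, 0.5, 0.8 and 1.0 SD become 17, 32, 58 and 74% with control pooled. The last row becomes 59% pooled and about 25% without control.

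**Two winners.** Hypotheses II and III overlap on secondary outcomes that were treatment goals. If ICF and NEFI are both at 0.5 and the other two arms at 0, both pooled tests on the same outcome are significant together in about 38% of trials at 52 per arm and 55% at 70. Both arms would then be called highest.

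**The other analyses.** ANOVA and the mixed-model F tests are omnibus and have no direction, so they cannot identify a highest arm. Tukey comparisons could, but the plan assigns them to differences outside its hypotheses. As written, they follow an ANOVA of three groups in a four-arm trial.

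**The case against.** The strongest reply has four parts.

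- **No sentence says that a significant pooled test alone licenses the word highest.** Tukey comparisons would put the ICF–TECH and ICF–NEFI differences for pre-post change beside it, so a tie or deficit would be visible. This is true, but no rule makes those differences decisive. Section 2.9 ties the pooled test, not Tukey, to Hypotheses II and III.
- **The equal-programme rows depend on pooling Group 4.** Several phrases, and 210 = 3 × 70, suggest three-group text to which a fourth arm was added. This stands: without control those rows fall to 5%. The tie (41%) and the worse-than-TECH cases (8% and 20%) remain.
- **The larger scenarios are generous.** The Introduction says most trials found similar gains in intervention and control groups, so control deficits of 0.8 to 1.0 SD are unlikely; at 0.1 to 0.2 SD the rate is 8 to 11%. The 41% and 20% cases put NEFI level with standard care. This stands as a caution about size, not about the logic.
- **An all-must-win rule costs power.** This also stands and bears on the choice of remedy.

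Two smaller points are fair. There is one such test per outcome and time point, not one overall. And Hypothesis I covers all outcomes, so Hypothesis II is not the only route to a conclusion on the primary outcomes.

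**Conclusion.** The concern holds. The pooled test is valid for showing that an arm is above the average of the others, and it keeps its 5% level when all arms are equal. It does not test whether the arm is highest, and no other planned analysis is given that task.

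This is so on either reading of the comparator. With ICF not uniquely best, the chance of a significant result in the assumed scenarios runs from 8 to 65% with control pooled. With control left out it is 5% when the programmes are equal, and 8 to 41% when ICF ties with or trails TECH. The rates assume 52–53 patients per arm, normal changes with SD 1 and the arm means shown; the documents give no arm-specific effects. The Wilcoxon fallback has the same limit, since it too compares one arm with a pooled distribution.

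**What to change.** State in section 2.9 whether the remaining participants include Group 4. Then choose one of two routes for Hypotheses II and III:

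- **Keep the superlative.** Claim it for ICF or NEFI only if that arm beats each other arm separately at one-sided .05. Because every comparison must succeed, α need not be split across the pairwise tests.
- **Reword the claim.** Leave Group 4 out of the comparator and claim that the arm is better than the average of the other two intensive programmes.

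In both cases run the ANOVA and Tukey comparisons on all four groups.

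The change to the text is small; the cost of the first route is power. Simulated at 52–53 per arm:

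| True lead of ICF | Beats each arm | Pooled, with control | Pooled, without control |
|---|---|---|---|
| 0.5 SD over both programmes, 1.0 SD over control | 71% | 99% | 90% |
| 0.5 SD over every arm | 64% | 93% | 90% |

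In the second case the all-must-win rule needs about 72 per arm (4 × 72 = 288) for 80% power, against 210 planned. The reworded claim keeps about 90% and is the cheaper route if the sample size cannot change.
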